Aim 1: Evaluate comparative effectiveness of two patient decision aids (a long PDA versus a short PDA) and a surgeon-focused intervention (usual care versus intervention, a summary that includes patients' goals and treatment preferences) on their ability to achieve high decision quality.

Hypothesis 1.1: Overall, patients who receive the long PDA will have higher decision quality than those who receive the short PDA.

Hypothesis 1.2: Patients who receive the long PDA, with more comprehensive information and videos to make the information more salient, will have higher knowledge scores than those who receive the short PDA.

Hypothesis 1.3: More patients who receive the short PDA, with the explicit values clarification exercise, will have a clear treatment preference than those who receive the long PDA.

Aim 2: Follow participants for 12 months to determine the impact of the decision support strategies on treatment choices and health outcomes, specifically, overall quality of life and functional status.

Hypothesis 2.1: Patients with high decision quality (i.e. informed and received preferred treatments) at one week will have better health outcomes at one year compared to those with low decision quality.

Hypothesis 2.2: Patients with high decision quality at one week will have lower surgical rates at one year compared to those with low decision quality.

Aim 3: Identify patient-, physician- and intervention-level factors associated with effectiveness for the PDAs. These factors include (1) patient characteristics (e.g. age, gender, education level, and joint (hip or knee)), (2) provider characteristics (e.g. years since graduation, surgical volume), (3) intervention compliance (e.g. whether patients reviewed the decision aids and amount of time spent reviewing the decision aids) and (4) mode of delivery (online or hardcopy).

BACKGROUND AND SIGNIFICANCE

Provide a brief paragraph summarizing prior experience important for understanding the proposed study and procedures.

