5. The staff at Health Decision Sciences Center will send the assigned decision aid, cover letter, information sheet, and appropriate survey (depending on provider assignment) to eligible patients in advance of their upcoming visit in the arthroplasty service. The letter will include information about how to opt-out of the study. The packet for subjects will include the survey (T1) so they have the option of completing the survey at home and bringing it with them to the visit.

6. Two days before the scheduled visit, study staff may call subjects who did not opt out to answer any questions about the study, and to remind them to review the decision aid before the visit, and complete the survey. Study staff can administer the survey over the phone if the patient prefers to do so.

7. On the day of the visit, the study staff will discuss the study with the eligible patients who did not opt-out. If the patient agrees to participate, then study staff will administer the survey either on paper or electronically if tablet or computer is available.

8. By completing this first assessment, participants will give consent to enroll in the study.

9. Study staff will work with the Harris Joint Registry at MGH and NWH data registry to download the completed quality of life and the study questionnaires for all participants.

10. The surgeon will receive the enhanced report (depending on their study assignment) for their participating patients.

11. A research coordinator will review medical record after the visit to complete the eligibility screener, as needed, and will send the second survey (T2) by mail or email within a week of the specialist visit to all confirmed eligible patients who did not opt out. If patients have not completed the routinely collected quality of life while at their visit, it will be included with this survey.

12. Study staff will follow-up with a phone reminder about one week after sending the survey, followed by a mailed reminder or up to three email reminders, and a second phone reminder for all the participants who did not complete the surveys. Participants who are receiving the survey by email will also get one mailed reminder if it is not completed in two weeks. Patients will be given the option to complete the survey by phone.

13. All participants who complete the T2 survey will receive a thank you note.

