3. Functional goals (T2, T3): participants will list the top three things that they need or want to do but are unable to do because of their knee or hip pain (at T2). Then at T3, they will indicate to what extent they are able to do those three things.

- 4. SURE scale (T2):** A brief, 4-item version of the widely used Decisional Conflict Scale (15) that measures patients' uncertainty about which treatment to choose and factors contributing to uncertainty (feeling uninformed, unclear values, and unsupported in decision making).
- 5. Decision regret (T3):** 5-item Likert scale that measures distress or remorse after a decision. A total score (0-100) is calculated with higher scores indicating more regret. The scale has demonstrated strong internal consistency (0.81-0.92) and correlates with decision satisfaction and quality of life (16).

Health Outcomes Measures (timing of use)

- 6. EQ-5D (T1, T3)** is a 6-item summary measure of health status for use in evaluating health and healthcare (17). It also generates a single index value for health status on which full health is assigned a value of 1 and death a value of 0. In conjunction with weights established for the 243 different combinations, the EQ-5D can be used to obtain quality-adjusted life years (18). The minimally important change is 0.1 points (19).
- 7. Knee injury and osteoarthritis score (KOOS) (T1, T3)** The KOOS and HOOS questionnaires were developed to assess the patients' opinions about their knee or hip and associated problems and have been used extensively (20-28). Three subscales, pain, symptoms and functional status will be used in this study. A normalized score (100 indicating no pain/symptoms and 0 indicating extreme pain/symptoms) is calculated for each subscale.
- 8. Harris Hip Score (HHS) (T1, T3):** The HHS assesses pain, function, range of motion and deformity for each hip. Pain receives 44 points, function 47 points, range of motion 5 points, and deformity 4 points for a total of 100 points. Function is subdivided into activities of daily living (14 points) and gait (33 points). The higher the HHS, the less dysfunction. A total score of 70 is considered a poor result; 70 – 80 is considered fair, 80 –90 is good, and 90 –100 is an excellent result. No normative values are available.

Additional items

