- 9. PDA use (T1, T2):** items will assess how much of the DVD, booklet and/or website was reviewed (all, some, a little, none) and how much time did they spend reviewing it (0-5 minutes; 6-10 minutes; 11-20 minutes; 21-30 minutes; >30 minutes).
- 10. Treatment received (T3, chart review):** surgical and non surgical treatments tried in the twelve months after the visit will be self reported by patients and also collected via chart review.
- 11. Expectations (T2, T3):** 4 items will assess expectations for pain relief, limitations in daily activities, overall success of surgery and complications (29).
- 12. Demographics (T2):** information such as education, employment, marital status will be self reported.
- 13. Satisfaction (T2, T3):** questions to assess overall satisfaction with quality of visit or treatment outcome
- 14. Information use (T3):** 1 question to assess what sources of information patient about their health condition they found important
- 15. IMPACT index (T2, T3):** 7 items assessing the impact of hip and knee osteoarthritis on patients' perception of their condition: worry, pain, limitation, confidence, and involvement in decision making.

Table 3: Measures including in surveys

Measures	Pre-visit (T1)	~ 1 week (T2)	~ Follow-up (T3)
Visit goals and functional goals	2 (physician intervention group only)		
		12	

Decision Quality Instrument	9		0
Decision aid use	1	1	Not asked
Decision making process	0	11	7
Functional goals	Not asked	2	1
SURE	Not asked	4	Not asked
Expectations	Not asked	10	10
Quality of life, pain and functioning (KOOS or HHS, EQ-5D)*	Routinely collected	Not asked	Routinely collected
Decision Regret	Not asked	Not asked	5
Satisfaction	Not asked	1	2
Demographics and treatment history		5	2
Health literacy	1	Not asked	Not asked
Impact Index	Not asked	7	7
Total number of items	13 (MD usual care group)/ 15 (MD intervention group)	53	34
Total time estimate	5 minutes	15 minutes	15 minutes

*These items are asked as part of routine care at this time point.

Randomization and blinding

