threshold *and* receive treatment that matches their preference. A logistic regression model with the generalized estimating equations (GEE) approach will be used to compare the rates of decision quality of the DA-A and DA-B groups and account for the clustering of patients within providers.[4] Analysis will start by testing the interaction between the two intervention factors. It is plausible that an interaction between DAs and type of surgeon report exists for this analysis. Thus, the effective sample size will be limited to 117 per group when the comparisons are stratified by the type of surgeon report. The study has 89% power to detect a difference in the percentage of patients with high decision quality of 18%, from 65% in DA-B group to 83% in DA-A group.

For hypothesis 1.2, an interaction between DAs and PPR report is unlikely so there is no need to account for clustering within the same provider, thus, we will use a two-sample t-test to compare the mean knowledge score between the two groups. With approximately 560 patients from each group, we can invoke the Central Limit Theorem and use a two-sample t-test to compare mean knowledge score between the two groups, even if the knowledge score is not normally distributed. The study will have 80% power to detect a difference as small as 3.3% in total knowledge scores assuming the SD is 20%. For hypothesis 1.3, patient's treatment preference will be assessed before the surgeon visit so again, there is no need to account for clustering. A X² test will be used to compare the percentage of patients with clear treatment preference between the two groups. Hypothesis 2.1 will use a linear regression model with the GEE approach and hypothesis 2.2 will use logistic regression with GEE approach to account for clustering of patients within surgeons for these analyses.

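### H2.1 compares later health outcomes between non-randomised groups, and the supplied SAP text names no baseline score or confounder although EQ-5D, KOOS and HHS are planned at T1

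*SAP*

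**What the plan says.** The protocol (Specific Aims, Aim 2) states H2.1 as: "Patients with high decision quality (i.e. informed and received preferred treatments) at one week will have better health outcomes at one year", compared with patients whose decision quality was low.

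The SAP gives the analysis in one clause: "Hypothesis 2.1 will use a linear regression model with the GEE approach". The reason it gives, shared with H2.2, is "to account for clustering of patients within surgeons for these analyses". The supplied text names no dependent variable, change score, baseline covariate or confounder for H2.1. Disease severity appears only in the SAP paragraph on heterogeneity, as a factor whose interaction with the interventions will be tested.

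Baseline health scores are planned. The protocol's Measures list gives EQ-5D at T1 and T3, and its next two entries open with "Knee injury and osteoarthritis score (KOOS) (T1, T3" and "Harris Hip Score (HHS) (T1, T3".

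On timing, Study Procedures step 11, which describes sending the T2 survey after the visit, adds: "If patients have not completed the routinely collected quality of life while at their visit, it will be included with this survey". Recruitment Procedures repeats this. The Table 3 row that begins "Quality of life, pain and functioning (KOOS or HHS, EQ-5D" marks these measures as not asked at T2.

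**The concern.** High decision quality means reaching the knowledge threshold and receiving the preferred treatment. Both are settled after randomisation, so random allocation does not balance the two groups, and the SAP's intention-to-treat statement cannot restore that balance.

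The protocol's own Background supplies a route for confounding. It says that the decision for surgery depends on clinical condition as well as informed preference, and that joint replacement very often relieves pain. Severity before the visit can therefore plausibly affect which treatment a patient receives, whether it matches the stated preference, and the score at T3. If the groups differ at T1, part of that difference persists to T3 and may be read as an effect of decision quality. If the high-quality group starts worse, a real benefit may be hidden.

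Two further choices are open. The plan does not say how the knee and hip instruments enter a linear model, or whether a quality-of-life form completed after the visit counts as baseline.

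**Working it through.** **No plan figure to reproduce.** In the supplied text H2.1 has no sample size, power, effect size or SD of its own. What follows illustrates the consequence of leaving out the baseline.

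**Inputs from the documents**
- EQ-5D minimally important change: 0.1 (protocol, Measures, item 6).
- Expected T3 completers: 716 (protocol, Research Design and Methods).
- Planning rates of high decision quality: 65% and 83% (SAP, H1.1); midpoint 74%.

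**Assumptions, not in the documents**
- Baseline EQ-5D gap between the groups: 0.03 to 0.10, sign unknown.
- Slope of T3 on T1: 0.3 to 0.6, taken equal to the correlation r (equal SDs at T1 and T3).
- EQ-5D SD 0.20; two-sided 5% test; clustering ignored.

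**Bias of an unadjusted T3 contrast** = baseline gap × slope.
- Low end: 0.03 × 0.3 = 0.009, or 9% of 0.1.
- Middle: 0.05 × 0.5 = 0.025, or 25% of 0.1.
- High end: 0.10 × 0.6 = 0.06, or 60% of 0.1. This pairs both upper limits, with a baseline gap as large as the important change itself.

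**What that does to the test.** With a 74/26 split of 716, the groups have about 530 and 186 patients. SE = 0.20 × √(1/530 + 1/186) = 0.0170. With no true effect, the chance of a significant result is P(|Z + bias/SE| > 1.96):

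| Gap | Slope | Bias | Bias/SE | Chance of p < 0.05 |
|---|---|---|---|---|
| 0.03 | 0.3 | 0.009 | 0.53 | 8% |
| 0.05 | 0.5 | 0.025 | 1.47 | 31% |
| 0.10 | 0.6 | 0.060 | 3.52 | 94% |

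**Gain in precision from adjustment.** Residual variance is multiplied by 1 − r², and the SE by its square root.
- r = 0.3: 0.91, SE ratio 0.95.
- r = 0.5: 0.75, SE ratio 0.87.
- r = 0.6: 0.64, SE ratio 0.80.

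The difference detectable with 80% power is (1.96 + 0.84) × 0.0170 = 0.048 unadjusted. Multiplying by these ratios gives 0.046, 0.041 and 0.038.

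**Instruments.** The protocol scores KOOS as three separate subscales, each from 0 to 100. It scores HHS as one total: pain 44 + function 47 + range of motion 5 + deformity 4 = 100. The shared range does not make them the same quantity, so a joint-specific analysis has to be stated.

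**Late forms.** Step 11 and Table 3 cannot both be complete descriptions of T2. T1 is the only scheduled earlier value of these scores. Unless forms are dated and flagged, a late form could serve as the covariate, or be carried forward as the T3 value in the SAP's LVCF sensitivity analysis.

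**The case against.** The strongest reply is that silence is not a plan. A reader might infer that the SAP commits to comparing raw follow-up scores with no baseline. It does not say so: no dependent variable is named, and the opening part of the SAP was not available and may contain outcome or covariate definitions. That stands, and the point is limited to the supplied text. The H2.1 sentence is nevertheless complete as it reads, and the only purpose it gives for the model is clustering.

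A reader might also infer that KOOS and HHS will be pooled. No section says this. Table 3 lists them as alternatives, and EQ-5D is common to both joints. The request is only that the plan settle the matter.

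A third tempting reading is that late forms are post-treatment and understate severity. The documents do not establish this. Step 11 is a catch-up for patients who missed the form, T2 is sent within a week of the visit, and no passage says that treatment has begun by then. NEBH includes these measures in its pre-visit survey and NWH offers completion by email beforehand, which limits the number affected. What stands is the conflict with Table 3 and the lack of a rule.

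Finally, the size rests wholly on assumed gaps and slopes. That is correct: the upper figure of 0.06 is an extreme of the assumed range, not an estimate.

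**Conclusion.** The concern holds as a gap in specification with a plausible bias. H2.1 contrasts non-randomised groups, and the supplied SAP text gives no baseline or confounder adjustment although T1 scores are planned. Run on that text alone, the comparison is open to confounding by baseline severity, in a direction the documents do not settle. The illustrated bias is 0.009 to 0.06 EQ-5D points against an important change of 0.1, under the assumed gap and slope; the false-positive chances also depend on the assumed SD and split, and ignore clustering. The documents do not show that an unadjusted analysis was chosen, that instruments are pooled, or that late forms shift the baseline in a known direction. Even with adjustment, H2.1 remains an observational association, because only measured confounding is reduced. The change should be made before analysis.

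**What to change.** In the SAP, for H2.1:
- Model T3 EQ-5D adjusted for T1 EQ-5D and joint.
- Within knees, model each T3 KOOS subscale, and within hips T3 HHS, each adjusted for its own T1 score.
- Add age, education, health literacy, site and the two intervention assignments as covariates. Treatment received is part of how decision quality is defined, so it should not be added as a routine covariate.
- Name one main outcome, EQ-5D or another, so that the several models do not compete.
- Keep GEE for clustering and report the result as an observational association.

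On baseline timing, reconcile step 11 (and its repeat in Recruitment Procedures) with Table 3. Record the completion date of each quality-of-life form, flag those completed after the visit, and repeat H2.1 without them.

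The cost is SAP wording, one date flag and one sensitivity run, with no new patient measurements. The main downside is that patients without a T1 score need a stated rule. Multiple imputation is now planned only as a sensitivity analysis; extending it to this model is one option.
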